### Brief summary:

This is a parallel-treatment, phase 2, randomized, double-blind study to assess the efficacy, safety, tolerability, PK, and PD of 20 mg twice daily (BID) oral SAR443820 compared with placebo in male and female participants aged 18 to 80 years with ALS followed by an open-label, long-term extension period.

Study ACT16970 consists of 2 parts (A and B) as follows:

Part A is a 24-week, double-blind, placebo-controlled part, preceded by a screening period of up to 4 weeks before Day 1.

On Day 1 of Part A, participants will be randomized in a 2:1 ratio to the SAR443820 treatment arm or matching placebo arm as listed below:

- Treatment arm: SAR443820, 20 mg, BID
- Placebo arm: Placebo, BID

Randomization will be stratified by the geographic region of the study site, region of ALS onset (bulbar vs other areas), use of riluzole (yes vs no), use of edaravone (yes vs no) and use of the combination of sodium phenylbutyrate and taurursodiol (named Relyvrio® in the USA and Albrioza® in Canada) (yes vs no). Participants will attend in-clinic study assessments at baseline (Day 1), Week 2, Week 4, Week 6, Week 8, Week 10, Week 12, Week 16, Week 20, Week 21, Week 22, Week 23 and Week 24. All ongoing participants at Week 24 will rollover to open-label extension (Part B). The Week 24 Visit is the end of Part A and the beginning of Part B.

Part B is an open-label, long-term extension period that starts from Week 24 and continues up to Week 106. The objectives of Part B are to provide extended access to SAR443820 participants in Part A and to further evaluate the safety and efficacy of long-term SAR443820 treatment. The treatment assignment of participants at randomization in Part A will remain blinded to Investigators, participants, and site personnel until the end of Part B. Every participant, except those who discontinue IMP treatment permanently in Part A, will receive BID oral tablets of 20 mg SAR443820 in Part B.

The study duration includes an up to 4-week screening period, 24-week double-blind treatment period in Part A, 80-week open-label treatment period in Part B, and 2-week post-treatment follow-up period, with a maximum total study duration of 110 weeks.

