### **Intervention groups and duration:**

Part A of the study will last for 24 weeks, and participants will receive 20 mg BID oral SAR443820 or placebo in a double-blind fashion for 24 weeks. All ongoing participants at Week 24 will rollover to open-label extension (Part B).

Part B begins at the end of Week 24 and continues up to Week 106. All participants, except those who discontinue IMP treatment permanently in Part A, will receive BID oral tablets of 20 mg SAR443820 in Part B.

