### *Investigational medicinal product(s) (IMP)*

- Formulation: Both SAR443820 and matched placebo will be formulated in tablets.
- Route(s) of administration: Tablets will be taken orally. The suggested method for investigational medicinal product (IMP) administration in detail is listed in [Section 6](#).

- Dose regimen:
  - Part A:
    - Treatment arm: SAR443820, 20 mg, BID
    - Placebo arm: Placebo, BID
  - Part B:
    - All participants: SAR443820, 20 mg, BID.

Based on a data review, in accordance with Data Monitoring Committee (DMC) recommendations leading to an urgent safety measure submitted on 05 December 2023, the sites have been instructed to pause the administration of SAR443820 in Part B (open-label extension) immediately. All participants in Part B will be encouraged to continue follow-up visits, but no doses of SAR443820 should be administered. Rollover to Part B for follow-up visits after completing Part A is also encouraged, but without taking SAR443820 in Part B. The decision of whether resuming SAR443820 administration in Part B will be made based on DMC recommendation when Part A data is available and benefit risk ratio will be evaluated.

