		Day 1		Week 2 (Day 15±3)	Week 4 (Day 29±3)	Week 6 (Day 43±3)	Week 8 (Day 57±3)	Week 10 (Day 71±3)	Week 12 (Day 85±3)	Week 16 (Day 113±3)	Week 20 (Day 141±3)	Week 21 (Day 148±3)	Week 22 (Day 155±3)	Week 23 (Day 162±3)	Week 24 (Day 169±3) a	
		Predose (baseline)	Postdose													
Visit	1 c	2		3	4	4.5	5	5.5	6	7	8	8.25	8.5	8.75	9	
Visit location or medium	Site	Site		Site	Site	Site d	Site	Site d	Site d	Site	Site d	Site d	Site d	Site d	Site	Site
Concomitant therapy and procedures recording		←-----→														X

Abbreviations: AE = adverse event; ALS = amyotrophic lateral sclerosis; ALSAQ-5 = Amyotrophic Lateral Sclerosis Assessment Questionnaire – 5; ALSFRS-R = Amyotrophic Lateral Sclerosis Functional Rating Scale – Revised; β-HCG = beta human chorionic gonadotropin; CHI3L1 = chitinase-3-like protein 1; C-SSRS = Columbia Suicide Severity Rating Scale; DTP = direct-to-patient; ECG = electrocardiogram; [REDACTED]; FSH = follicle stimulating hormone; [REDACTED] HIV = human immunodeficiency virus; IFNy = interferon γ; IL = interleukin; IMP = investigational medicinal product; IP-10 = interferon gamma-induced protein 10; MCP = monocyte chemoattractant protein; MIP1 = macrophage inflammatory protein-1; NfL = neurofilament light chain; p75ECD = extracellular domain of p75; PK = pharmacokinetic(s); SAE = serious adverse event; sTREM2 = soluble triggering receptor expressed on myeloid cells 2; SVC = slow vital capacity; TARC = thymus- and activation-regulated chemokine; TNF = tumor necrosis factor; WOCBP = woman of childbearing potential

- a The Week 24 visit is considered as both the last visit for Part A and the first visit for Part B. For all participants, last dose of double-blind IMP should be taken on the day prior to the Week 24 visit. Week 24 visit will consist of first open-label (Part B) IMP. All assessments for end of Part A should be completed prior to first dose of open-label IMP.

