- b For participants who prematurely discontinue IMP, the early discontinuation visit will happen 2 weeks (±3 days) after the last dose of the IMP. If, after the early IMP discontinuation visit, participants decide to continue the study, they will follow the same schedule for visits, but only ALSFRS-R, SVC, blood samples for plasma sTREM2, blood samples for serum biomarkers, including NfL, CHI3L1, cytokine and chemokine panel and urine sample for biomarker analysis (p75ECD), vital signs, physical examination, neurological examination, AE review, SAE review and concomitant therapy and procedures recordings will be performed in the visits, as applicable according to the schedule of activities.
- c The screening visit can be performed over up to 2 days if needed (they do not need to be consecutive days) to minimize the burden on participants.
- d Alternatively, the Week 6, Week 10, Week 12, Week 20, Week 21, Week 22, and Week 23 visit can be conducted by phone. If the study visit is conducted by phone, the blood sample must be collected at a local clinic or at home by a nurse, and the sample must be tested at a local lab or the central lab. In case of testing at a local lab, the study site staff must contact participants, within 2 working days after the results are expected to be available, to collect results of blood test.; For Week 12, and Week 20 visit, if conducted by phone, 1) the urine pregnancy test will be provided directly to participants and self-conducted at home. The study site staff will call the participants to remind them to conduct the pregnancy test and collect the result. If pregnancy test result is positive, participant should discontinue IMP immediately; 2) ALSFRS-R will be measured through the phone call.
- e Participants will be randomized in a 2:1 ratio to the SAR443820 treatment arm or placebo arm. The randomization will be stratified by the geographic region of the study site, region of ALS onset (bulbar vs other areas), use of riluzole (yes vs no), and use of edaravone (yes vs no) and use of the combination of sodium phenylbutyrate and taurursodiol (yes vs no).
- f In addition to the IMP being dispensed in the clinic, the IMP may be dispensed for home administration via DTP services, except if prohibited by local regulatory authorities.
- g Only IMP reconciliation will be done at this visit.

- h* Reconciliation of the IMP dispensed in Part A and dispensation of the open-label IMP in Part B at this visit (Week 24).

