### 1.3.2 Part B

Procedure b	Intervention period (Part B) a												Last follow-up visit c	Early IMP discontinuation visit e
	Week 28 (Day 197±3)	Week 30 (Day 211±3)	Week 32 (Day 225±3)	Week 34 (Day 239±3)	Week 36 (Day 253±3)	Week 40 (Day 281±3)	Week 44 (Day 309±3)	Week 52 (Day 365±3)	Week 64 (Day 449±3)	Week 76 (Day 533 ±3)	Week 88 (Day 617 ±7)	Week 104 (Day 729 ±7)		
Visit	10	10.25	10.5	10.75	11	11.5	12	13	14	15	16	17	18	
Visit location or medium	Site	Site d	Site d	Site d	Site	Site d	Site	Site	Site	Site	Site	Site	Site	Site
Study intervention dispensing and reconciliation f	X				X		X	X	X	X	X	X g		X g
Physical examination h	X				X		X	X	X	X	X	X	X	X
Neurological examination i	X				X		X	X	X	X	X	X	X	X
Laboratory tests for hematology and chemistry	X	X j	X j	X j	X	X j	X	X	X	X	X	X	X	X
12-lead ECG	X				X			X		X		X	X	X
C-SSRS questionnaire k	X				X		X	X	X	X	X	X	X	X
Vital signs l	X				X		X	X	X	X	X	X	X	X
Weight	X				X		X	X	X	X	X	X	X	X
SVC	X				X		X	X	X	X	X	X		X
ALSFRS-R	X				X		X	X	X	X	X	X		X
ALSAQ-5	X				X		X	X	X	X	X	X		X
Blood sample for plasma PK	X m													

Abbreviations: AE = adverse event; ALSAQ-5 = Amyotrophic Lateral Sclerosis Assessment Questionnaire-5; ALSFRS-R = Amyotrophic Lateral Sclerosis Functional Rating Scale – Revised;  $\beta$ -HCG = beta human chorionic gonadotropin; C-SSRS = Columbia Suicide Severity Rating Scale; DTP = direct-to-patient; ECG = electrocardiogram; [REDACTED];

IMP = investigational medicinal product; Nfl = neurofilament light; PK = pharmacokinetic(s); SAE = serious adverse event; SVC = slow vital capacity; WOCBP = woman of childbearing potential

a An urgent safety measure was submitted on 05 December 2023 to request pause of SAR443820 administration in Part B (open-label extension) immediately. All participants in Part B will be encouraged to continue follow-up visits, but no doses of SAR443820 should be administered until DMC recommendation to resume dosing based on benefit-risk considerations when Part A data is available.

b The first visit for Part B is the Week 24 Visit in Part A

- b The first visit for Part B is the Week 24 visit in Part A.
- c The last follow-up visit will happen 2 weeks ( $\pm 3$  days) after Week 104 visit (Visit 17).

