## 8 STUDY ASSESSMENTS AND PROCEDURES

- Study procedures and their timing are summarized in the SoA ([Section 1.3](#)). Protocol waivers or exemptions are not allowed.
- Adherence to the study design requirements, including those specified in the SoA, is essential and required for study conduct.
- All screening evaluations must be completed and reviewed to confirm that potential participants meet all eligibility criteria. The Investigator will maintain a screening log to record details of all participants screened and to confirm eligibility or record reasons for screening failure, as applicable.
- Procedures conducted as part of the participant's routine clinical management (eg, blood count, urine tests) and obtained before signing of the ICF may be utilized for screening or baseline purposes provided the procedures met the protocol-specified criteria and were performed within the time frame defined in the SoA.
  - Repeat or unscheduled samples may be taken for safety reasons or for technical issues with the samples.
  - If onsite visits are not feasible (due to ALS progression, increased monitoring for AE follow-up), remote visits (eg, with home nurses, a home health vendor, a local clinic etc.) may be planned for the collection of safety and/or efficacy data.

For a regional or national emergency declared by a governmental agency, contingency measures are included in Appendix 9 ([Section 10.9](#)).

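### Part A schedule footnotes a and h still call for open-label dispensing and a first open-label dose at Week 24 while Part B dosing is paused

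*Protocol*

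**What the plan says.** **Part A schedule (Protocol 1.3.1).** The Week 24 column appears only in this table. Its dispensing cell carries footnote h: "Reconciliation of the IMP dispensed in Part A and dispensation of the open-label IMP in Part B at this visit (Week 24". Footnote a, attached to the Week 24 column heading, says "Week 24 visit will consist of first open-label (Part B) IMP" and places the end-of-Part-A assessments before that dose. No footnote to this table mentions the pause. Footnote g, used in the same row for Week 2 and the early discontinuation visit, reads "Only IMP reconciliation will be done at this visit".

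**The pause.** The synopsis (IMP paragraph) says "Rollover to Part B for follow-up visits after completing Part A is also encouraged, but without taking SAR443820 in Part B". Sections 4.1 and 7.1.2 say the same. Footnote a of the Part B schedule (1.3.2) says "no doses of SAR443820 should be administered until DMC recommendation to resume dosing based on benefit-risk considerations when Part A data is available". Footnote b of that table makes Week 24 the first Part B visit.

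**Status of the schedule (Protocol 8).** "Adherence to the study design requirements, including those specified in the SoA, is essential and required for study conduct".

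**Time off drug.** Section 7.1.1 makes permanent discontinuation mandatory once IMP has been stopped for more than 8 cumulative weeks in Part B. Section 7.1.2 caps a temporary stop at the same 8 weeks. That section also describes the pause, with no end date and with restart left to a DMC recommendation once Part A data are available. Sections 7.1.1, 7.1.2 and 7.1.2.1 contain no exemption for the pause.

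**The concern.** Two current instructions in one protocol point in opposite directions for the same visit. The one that permits dosing sits in the table a site would open to run that visit. The drug was paused because of an identified liver-injury risk, including two SUSARs with bilirubin above 2 × ULN (Protocol 2.3.1). A site working only from the Week 24 column would dispense open-label tablets and start them. For a participant randomised to placebo, that would be the first exposure to SAR443820, begun during a safety pause.

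The 8-week limit raises a smaller question. The protocol keeps open a restart on DMC advice, yet its mandatory stopping rule has no carve-out for a stop that the sponsor itself ordered.

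**Working it through.** There is no planned figure to reproduce. The check compares the texts and then does date arithmetic.

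**1. Do the texts conflict?**
- Part A footnotes a and h, with the Week 24 cell: dispense open-label IMP and take the first dose at Week 24.
- Synopsis IMP paragraph, 4.1, 7.1.2 and Part B footnote a: no Part B doses. The first three expressly cover participants who finish Part A after the pause.
- Both sets are current text. Amendment 05 edited this Part A table (it added Weeks 21 to 23 and revised footnotes b and p). Its summary lists 1.1, 1.2, 1.3.2 and 4.1 as changed for the pause, but not 1.3.1. That pattern fits an edit that was not carried through.

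**2. Was anyone still due a Week 24 visit?** The Amendment 05 summary says that all participants had passed Week 19 by 5 December 2023 and refers to participants still in Part A.
- Week 19 is Day 1 + 7 × 19 = Day 134. Week 24 is Day 169.
- Longest remaining time: 169 − 134 = 35 days.
- 5 December 2023 + 35 days = 9 January 2024; with the +3-day window, 12 January 2024.
- From the amendment date, 13 December 2023: 27 days to 9 January, 30 days to 12 January.

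Week 24 visits could therefore still fall due after the amendment was issued.

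**3. Who would be affected?** The number is not given. At the planned allocation (174 to SAR443820, 87 to placebo), the placebo share is 87/261 = 0.333, or about one third, if the remaining participants mirror the overall ratio.

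**4. The 8-week limit (conditional).**
- Participant dosing in Part B on 5 December 2023, with no earlier interruption: 5 December + 56 days = 30 January 2024. Earlier Part B interruptions would bring this forward.
- Gap from the latest Week 24 visit: 30 January − 9 January = 21 days, or 18 days from 12 January.
- If the limit were also counted from Week 24 for the last participant to roll over: 9 January + 56 days = 5 March 2024.

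For the first group, Part A lock, analysis and DMC advice would have to fit within about 18 to 21 days for dosing to resume inside the limit.

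**The case against.** The strongest reply is that the protocol already settles the case. Three sections address exactly the participants finishing Part A and say that they take no drug. Part B footnotes a and b, read together, reach Week 24, and the dose in Part A footnote a is itself labelled a Part B dose, so the bar covers it on its own terms. Section 8 does not rank the footnotes above the pause: it binds sites to the study design as a whole, including the Part B schedule. Sites were also told directly on 5 December 2023. This stands as far as likelihood goes: a reader might infer that participants were, or probably would be, dosed at Week 24 during the pause, and the documents do not support that. It does not remove the contradiction, because the answer is reached only by cross-reference from a table that says the opposite.

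Two other stronger readings also fail. The synopsis states in Brief summary, "Every participant, except those who discontinue IMP treatment permanently in Part A, will receive BID oral tablets of 20 mg SAR443820 in Part B", and again under Intervention groups and duration, without a caveat. A reader might count these as further wrong dosing rules. The same synopsis gives the pause shortly afterwards, so aligning them is editorial only.

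A reader might also infer that the 8-week rule bars any restart. That needs two things the documents do not establish: that dosing resumes after the limit has passed, and that an ordered pause counts as an IMP discontinuation. Section 7.1.2 opens with stops considered by the investigator and gives the pause its own paragraph and restart route, which suggests no intent to discontinue everyone. What remains is an unclear rule that one sentence would settle.

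**Conclusion.** The point holds for Part A footnotes a and h: they state a Week 24 dosing and dispensing rule that is wrong while the pause is in force. It should be fixed because it concerns liver safety. The nominal period runs from 5 December 2023 to 9 January 2024 (12 January with the window), or 27 to 30 days from the amendment date. This assumes visits on schedule and a last participant only just past Week 19; if that participant was further on, the period ends sooner. Dates of local adoption of Amendment 05 are not given.

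The 8-week point is secondary and conditional. Follow-up, data collection, sample size, error control and the comparison by randomised group are unaffected by either point.

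**What to change.** Add to Part A footnotes a and h the overlay that Part B footnote a already uses. For example: *While the pause of 5 December 2023 is in force, only IMP reconciliation is done at Week 24; no open-label IMP is dispensed or taken until dosing is resumed on DMC recommendation.* An overlay is preferable to replacing footnote h with g in the Week 24 cell, because it need not be reversed if dosing resumes.

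Add one sentence to 7.1.2, cross-referenced from 7.1.1, saying that the ordered pause does not count toward the 8-week cumulative limit in Part B. When the text is next opened, align the two synopsis statements.

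The drafting cost is a few sentences. The change would follow the approval route in Protocol 10.1.1, which excepts changes needed to remove an immediate hazard. No assessment, data item or analysis changes.

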Laboratory tests for hematology and chemistry	X	X		X	X	X p	X	X p	X p	X	X p	X p	X p	X p	X	X

Procedure	Screening (up to 4 weeks before Day 1)	Intervention period (Part A)													Early IMP discon- tinuation visit b	
		Day 1		Week 2 (Day 15±3)	Week 4 (Day 29±3)	Week 6 (Day 43±3)	Week 8 (Day 57±3)	Week 10 (Day 71±3)	Week 12 (Day 85±3)	Week 16 (Day 113±3)	Week 20 (Day 141±3)	Week 21 (Day 148±3)	Week 22 (Day 155±3)	Week 23 (Day 162±3)	Week 24 (Day 169±3) a	
		Predose (baseline)	Postdose													
Visit	1 c	2		3	4	4.5	5	5.5	6	7	8	8.25	8.5	8.75	9	
Visit location or medium	Site	Site		Site	Site	Site d	Site	Site d	Site d	Site	Site d	Site d	Site d	Site d	Site	Site
Blood draw for optional DNA collection				X g	X g											
SVC	X	X					X			X						X
ALSFRS-R	X	X			X		X		X	X	X					X
ALSAQ-5		X					X			X						X
Muscle strength r			X					X			X					X
Blood sample for plasma PK t				X u	X v			X v, w								
Blood samples for plasma sTREM2	X	X						X			X					X

Procedure	Screening (up to 4 weeks before Day 1)	Intervention period (Part A)													Early IMP discon- tinuation visit b	
		Day 1		Week 2 (Day 15±3)	Week 4 (Day 29±3)	Week 6 (Day 43±3)	Week 8 (Day 57±3)	Week 10 (Day 71±3)	Week 12 (Day 85±3)	Week 16 (Day 113±3)	Week 20 (Day 141±3)	Week 21 (Day 148±3)	Week 22 (Day 155±3)	Week 23 (Day 162±3)	Week 24 (Day 169±3) a	
		Predose (baseline)	Postdose													
Visit	1 c	2		3	4	4.5	5	5.5	6	7	8	8.25	8.5	8.75	9	
Visit location or medium	Site	Site		Site	Site	Site d	Site	Site d	Site d	Site	Site d	Site d	Site d	Site d	Site	Site
Blood samples for serum biomarkers, including NfL, CHI3L1, cytokine and chemokine panel x	X	X					X			X					X	X
Urine sample for biomarker analysis (p75ECD) y	X	X					X			X					X	X
Urine sample for urinalysis	X	X		X	X		X			X					X	X
Blood sample for archiving		X														
AE review			←-----→													X
SAE review			←-----→													X

Procedure	Screening (up to 4 weeks before Day 1)	Intervention period (Part A)													Early IMP discon- tinuation visit b	

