#### Handling of participants after permanent intervention discontinuation

If a participant is withdrawn from study intervention permanently, the Sponsor will be notified within 2 business days and the date and reason(s) for the withdrawal will be documented by the Investigator in the appropriate pages of the eCRF when considered as confirmed.

Participants who prematurely discontinue the IMP will be encouraged to complete the rest of study visits for safety and efficacy assessments up to and including the last scheduled visit (Week 106). A separate PK sample may be taken if appropriate. At a minimum, participants should complete an early discontinuation visit 2 weeks after the last IMP dosing. All withdrawn participants will be followed until resolution of all their AEs or until the unresolved AEs are judged by the Investigator or Sponsor to have stabilized (see [Section 10.3.3](#)).

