	Change from baseline in slow vital capacity (SVC) (muscle strength, Amyotrophic Lateral Sclerosis Assessment Questionnaire (ALSAQ-5), serum neurofilament light chain (NfL)) to Week 24	ITT	Permanent study intervention discontinuation before Week 24 – regardless of treatment discontinuation (treatment policy)		These secondary endpoints will be analyzed using MMRM with change from baseline value up to Week 24 as response variable, and treatment, visit, randomization strata of the geographic region of the study site, ALS onset region (bulbar or other areas), use of riluzole (yes or no), use of edaravone (yes or no), use of the combination of sodium phenylbutyrate and taurursodiol (yes or no), treatment-by-visit interaction, disease duration (from first symptom onset to the screening visit), baseline value of the endpoint, baseline NfL (if different from the baseline value of the endpoint), disease duration-by-visit interaction, baseline value of the endpoint-by-visit interaction and

Endpoint Category (estimand)	Endpoint	Population	Intercurrent event(s) handling strategy	Estimands	Population-level summary (Analysis and missing data handling)
				baseline NfL-by-visit interaction (if different from the baseline value of the endpoint-by-visit interaction) as covariates. All available data will be used, and missing data will be handled by MMRM based on missing at random assumption. For muscle strength data, if there is a missing value for one muscle measurement which continues to have the missing value through the final assessment (eg, at least 2 consecutive missing values up to the final assessment), then these missing values for this muscle measurement will be imputed as zero; all the other missing values will not be imputed.	

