3.3.1.2 Main analytical approach

Treatment policy will be used for the analyses of all secondary endpoints in Part A and Part B as stated in [Table 2](#).

CAFS

CAFS at Week 24, Week 76 and Week 104 will be analyzed in the same manner as that used to analyze the primary endpoint in Part B in [Section 3.2.2](#).

Continuous Endpoints

Continuous endpoints include:

Part A

- change from baseline in SVC to Week 24
- change from baseline in muscle strength to Week 24
 - change from baseline in megascore to Week 24
 - change from baseline in grip strength to Week 24
- change from baseline in ALSAQ-5 to Week 24
- change from baseline in serum NfL to Week 24

Part B

- change from baseline in the ALSFRS-R total score to Week 52, Week 76, and Week 104
- change from baseline in SVC to Week 52, Week 76, and Week 104
- change from baseline in ALSAQ-5 to Week 52, Week 76, and Week 104
- change from baseline in serum NfL to Week 52

These continuous endpoints will be analyzed using the same manner as that used to analyze the primary endpoint in Part A in [Section 3.2.2](#), except that baseline ALSFRS-R score will be replaced by the baseline value of the corresponding endpoint. Plots of least squares means (\pm standard error) over time will be provided. Plots of mean (\pm SD) and/or mean change (\pm SD) and/or median over time will also be provided. For NfL data, log transformation will be applied in

the MMRM model. The treatment difference will then be back-transformed to the original scale. The back-transformed LS means stand for geometric mean ratios compared to baseline, and the back-transformed LS means difference stands for ratio of the geometric mean ratios compared to baseline between SAR443820 and placebo. In order to assess the impact of deviation from the normality assumption, a sensitivity analysis using rank analysis of covariance (ANCOVA) with the same covariates as for the MMRM analysis except visit and related interaction terms, will be performed to provide the p-value for the comparison between the treatment groups.

Time-to-event endpoints

Time-to-event endpoints in Part B include:

[figure not shown]
- time from baseline to occurrence of either death or permanent assisted ventilation (>22 hours daily for >7 consecutive days), whichever comes first
- time from baseline to the occurrence of death

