3.5 MULTIPLICITY ISSUES

To control the Type 1 error rate for the study, a hierarchical testing procedure will be applied at a 2-sided 5% significance level for primary and selected secondary endpoints in Part A, ie, each hypothesis will be formally tested only if the preceding one is significant at the 5% level. If

SAR443820 is significant for the primary endpoint in part A, a selective set of secondary endpoints in Part A will be tested following the hierarchical testing procedure shown below:

- CAFS score at Week 24
- Change from baseline in ALSAQ-5 to Week 24
- Change from baseline in serum NfL to Week 24
- Change from baseline in SVC to Week 24
- Change from baseline in megascore to Week 24

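### Protocol footnote b drops ALSAQ-5 and muscle strength after the early discontinuation visit, although the SAP tests both at Week 24 by treatment policy and could score the missing muscle values as zero

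*Protocol*

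**What the plan says.** **Collection.** Protocol 1.3.1 footnote b sets what is done once a participant has stopped drug, attended the early discontinuation visit and chosen to stay: "they will follow the same schedule for visits, but only ALSFRS-R, SVC, blood samples for plasma sTREM2, blood samples for serum biomarkers", then a urine biomarker, vital signs, examinations, adverse events and concomitant therapy. The list is closed and contains neither ALSAQ-5 nor muscle strength. On timing, "the early discontinuation visit will happen 2 weeks (±3 days) after the last dose of the IMP". Protocol 7.1.1 carries no such limit: "Participants who prematurely discontinue the IMP will be encouraged to complete the rest of study visits for safety and efficacy assessments".

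**Analysis.** SAP Table 2 (section 1.2.1) handles stopping drug as "Permanent study intervention discontinuation before Week 24 – regardless of treatment discontinuation (treatment policy" for SVC, muscle strength, ALSAQ-5 and NfL, with MMRM under missing at random. SAP 3.3.1.2 repeats it: "Treatment policy will be used for the analyses of all secondary endpoints in Part A and Part B". In SAP 3.5, "a hierarchical testing procedure will be applied at a 2-sided 5% significance level for primary and selected secondary endpoints in Part A"; the second secondary test is "Change from baseline in ALSAQ-5 to Week 24" and the fifth is megascore. Grip strength is outside the sequence.

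**Zero rule.** SAP 3.3.1.1 sets a muscle measurement to zero when it is missing at a visit and stays missing through the final assessment. The example given is at least two consecutive missing values. Other missing values are not imputed. The rule does not ask why the value is missing.

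**The concern.** A treatment-policy estimand needs outcomes measured after drug is stopped. For two of the five secondary tests, the schedule tells sites not to take them beyond the early discontinuation visit. The MMRM then fills Week 24 from values up to that visit, so the contrast moves toward the effect had these participants stayed on drug, while still labelled treatment policy.

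Muscle strength carries a second problem. The zero rule makes sense for a muscle too weak to test. It has no exception for a test skipped because the protocol did not ask for it, so a participant who is present and able to perform the test could be scored as having no strength.

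Stopping is foreseeable: Protocol 7.1.1 makes it mandatory for liver stopping criteria, for more than 2 weeks of cumulative interruption in Part A, and for starting a standard-of-care ALS drug in Part A.

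**Working it through.** The plan states no figure for lost ALSAQ-5 or muscle data, so there is none to reproduce. The sample size of 261 concerns the primary endpoint and does not bear on this point.

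**1. Which secondary tests lose data**

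| Order in SAP 3.5 | Week 24 endpoint | Still collected under footnote b? |
|---|---|---|
| 1 | CAFS | Yes, through ALSFRS-R |
| 2 | ALSAQ-5 | No |
| 3 | Serum NfL | Yes |
| 4 | SVC | Yes |
| 5 | Megascore | No |

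**2. Which stoppers would meet the zero rule.** The row "Muscle strength r" in the schedule is shifted in the available text. By analogy with the biomarker row, I read it as Day 1, Weeks 8, 16 and 24, and the early discontinuation visit. Let s be the week of the last dose, so the discontinuation visit falls at s + 2.

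- If that visit's value is not allocated to a scheduled visit, Weeks 16 and 24 are both missing when s + 2 < 16, so s < 14. Only Week 24 is missing for s from 14 to just under 22.
- If it is allocated to the nearest scheduled visit (midpoint windows are my assumption, because SAP Table 7 is not shown), both are missing when s + 2 < 12, so s < 10. Only Week 24 is missing for s from 10 to just under 18.
- With stops spread evenly over 24 weeks (assumption), 10/24 = 42% to 14/24 = 58% of stoppers who stay in the study meet the two-value example, and 8/24 = 33% lose Week 24 only.

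These shares ignore the date on which footnote b was edited.

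**3. The date.** The Protocol's summary of changes says that Amendment 05 (13 December 2023) edited footnote b, and that all participants had passed Week 19 by 5 December 2023. Weeks 8 and 16 were then behind everyone, so the edited text can itself remove only Week 24. One missing value falls short of the two-value example unless Week 16 was already missing. What footnote b required before Amendment 05 is not in the documents.

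**4. Size of one imputed zero.** For each muscle, Z = (0 - mean)/SD, using the 18 means and SDs in SAP 3.3.1.1. The extremes are right shoulder flexion, -14.01/4.11 = -3.41, and right ankle dorsiflexion, -17.45/7.03 = -2.48. The average over all 18 is **-2.90**. A skipped session loses all 18 muscles at once, so this is the relevant value.

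**5. Effect on the contrast.** On simple arm means:

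spurious difference = (difference in trigger rate) × (imputed change - true change)

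Assume trigger rates of 8% and 4%, a true change of -0.5 in both arms, and a baseline megascore from -0.5 to -2.0.

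- Imputed change = -2.90 - baseline, so -2.40 to -0.90.
- Baseline -0.5: 0.04 × (-2.40 + 0.50) = -0.08.
- Baseline -2.0: 0.04 × (-0.90 + 0.50) = -0.02.
- Equal trigger rates: 0.

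**The case against.** The strongest reply is about timing. The edited footnote can remove at most Week 24. Someone just past Week 19 on 5 December 2023 reaches Week 24 about five weeks later, around 9 January 2024, and SAP version 2 is dated 8 January 2024. Changing the footnote therefore recovers few values. This stands, and it makes the SAP wording the more useful repair.

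A reader might infer that there are no off-drug data at all. The documents do not support that: the restriction begins after a visit held 2 weeks after the last dose, and both measures appear to be taken there. That value may also fill a scheduled window.

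A reader might also infer that the schedule zeroes the muscle score of everyone who stops. It does not. Under the SAP's own example, only stoppers with two or more trailing missing values are zeroed. Later stoppers lose Week 24 alone. Because the two-value condition is introduced only as an example, it is unclear whether one missing final value would count.

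Finally, missing at random is openly declared, ALSAQ-5 is reached only if the primary endpoint and CAFS succeed, and megascore comes last. That limits the consequence. It does not reconcile footnote b with Protocol 7.1.1 or SAP Table 2.

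**Conclusion.** The mismatch is real at the tested time point. After the early discontinuation visit, Part A footnote b collects neither ALSAQ-5 nor muscle strength, while the SAP declares a treatment-policy analysis of both at Week 24. For these participants the two contrasts rest on values up to that visit and do not fully estimate the stated effect. Where two or more trailing muscle values are missing, a test not done by instruction would be scored as 0 kg, a megascore of -2.90.

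The number of such zeros is unknown. Without the pre-amendment text of footnote b, zeros caused by the schedule can be neither shown nor excluded. The 0.02 to 0.08 is an illustration under assumed trigger rates of 8% and 4%; it vanishes if the rates are equal.

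Given the identified liver risk, a reader might infer that the bias runs against SAR443820. That is plausible, but the documents give no stopping rates by arm, and Protocol 2.3.3 describes the liver data as blinded.

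The primary endpoint, CAFS, NfL and SVC keep their inputs, and Protocol 9.1 declares the study positive on the primary endpoint alone. This deserves correction before Part A database lock but does not threaten the main result. Alpha and sample size are unchanged.

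**What to change.** 1. **Protocol 1.3.1, footnote b.** Reconcile it with Protocol 7.1.1 and SAP Table 2 by adding ALSAQ-5 and muscle strength at the visits where the schedule already places them. In practice that means Week 24 for anyone still to reach it.
2. **SAP 3.3.1.1 and Table 2, before Part A database lock.** Apply the zero rule only to muscles that could not be tested because of weakness. Treat values not collected because of footnote b as missing. Use the same wording for grip strength.
3. **Single missing Week 24 value.** Replace the example with a definite condition that says how this case is handled.
4. **Reporting.** Give, by arm, the number of ALSAQ-5 and muscle values not collected because of footnote b and the number of zeros imputed. State that for these participants the two contrasts rely on data up to the early discontinuation visit.

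The cost is one line in the footnote and a few sentences in the SAP. For participants it is a questionnaire of about 5 minutes plus dynamometry, at visits they already attend for ALSFRS-R and SVC.
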